12.4.2. Pregnancy

Pregnancies that occur from the time that informed consent is signed through 30 days following the last dose of the study medication will be collected and reported on the Pregnancy Event Form.

If a subject or a subject’s partner becomes pregnant during the course of the study, they will be instructed to report the pregnancy to the Investigator (see below). All female pregnant subjects will be instructed to commence discontinuation of the study medication. Further, the subject (or female partner of male subject) will be requested to return promptly/within 48 hours of the first notification of pregnancy to the study center and undergo a serum/urine pregnancy test, as confirmation of pregnancy. If positive, the female pregnant subject will no longer receive any additional study medication. All pregnancies, whether or not the subject received any additional study medication, will be followed until resolution (ie, termination [voluntary or spontaneous] or birth).

To report a pregnancy, the Pregnancy Event Form must be completed and sent via fax to PPD- PVG within 1 business day of the Investigator or study center staff becoming aware of the pregnancy. The Sponsor provides the Pregnancy Event Form.

Pregnancy itself is not regarded as an AE unless there is a suspicion that the study drug may have interfered with the effectiveness of a contraceptive medication or other AEs were detected.

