- ^f Includes clinical chemistry, hematology and urinalysis. Estimated creatinine clearance using Cockcroft-Gault equation at Screening only.
- ^g Required for subjects of Asian ancestry (or subjects for whom the absence of Asian ancestry cannot be confirmed) and who do not have documentation to show that they are not carriers of HLA-B*1502.
- ^h Subjects who provided optional separate informed consent/assent only.
- ⁱ A serum pregnancy test will be given to all female subjects of childbearing potential at screening. An on-site urine pregnancy test will be given to all female subjects of childbearing potential at Visits 1-8. Any positive urine pregnancy test will be followed up with a serum test for confirmation of pregnancy. A serum pregnancy test will be given to all females subjects of childbearing potential at Visit 9 (EOS) or at the EDV.
- ^j The Liverpool Adverse Event Profile collects information on AEs associated with AEDs.
- ^k Subjects who elect to continue on commercially available drug will not be dispensed additional ESL at this visit. Subjects who elect to discontinue ESL will be provided sufficient ESL to accommodate the appropriate taper regimen.
- ^l Subjects will be provided with the Empatica watch and instructed in the use of the watch.
- ^m Subjects will be provided a standardized paper daily seizure diary and an electronic daily seizure diary and instructed in the use of the diaries. Diaries are to be completed daily whether a seizure occurs or not.
- ⁿ The “Baseline/Screening” (lifetime) version should be administered at the screening visit and the “Since Last Visit” version at all other time points.
- ^o The screening visit should take place 7 - 10 days prior to the titration visit, and may be extended to 7 – 17 days if required with consent of medical monitor. Subjects of Asian ancestry who require HLA-B*1502 testing (eg, do not have prior test results) may have the screening visit 7 - 17 days prior to the titration visit.
- ^p Subjects who discontinue prior to the EOS visit will be provided sufficient ESL to accommodate the appropriate taper regimen.
- ^q At the Safety Follow-Up visit, the standardized paper daily seizure diary will not be collected; however it will be reviewed as part of the subject's safety assessments.

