10.1.2. Premature Discontinuation of Treatment with Study Drug

Subjects who prematurely discontinue treatment with ESL prior to Visit 9 (EOS) for any reason will be gradually tapered off study drug (see Table 5). However, abrupt discontinuation of the drug is permitted for the treatment of an AE. Subjects who prematurely discontinue treatment with ESL (abruptly, or by taper) will be withdrawn from the study.

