13. TERMINATION OF SUBJECT FROM STUDY

Subjects may terminate the study participation at any time for any reason.

Subjects may be discontinued from the study at any time for any of the following reasons:

- Adverse event.
- Lack of efficacy (specify).
- Withdrawal by subject (specify).
- Withdrawal by Investigator (specify).
- Protocol deviation (specify).
- Study terminated by Sponsor.
- Death.
- Pregnancy (subject or subject's partner).
- Other (specify).

If at any time during the course of the study, in the opinion of the Investigator, the subject may no longer safely participate due to a change in medical status (eg, experiences an AE, becomes pregnant), the subject must be discontinued from the study.

Subjects may discontinue the study at any time due to worsening of seizures, intolerance, or other reasons.

Subjects who discontinue the study will undergo taper of study drug, unless abrupt discontinuation of the drug is required in response to an AE (eg, rash).

Subjects who experience an intolerable AE at the lowest dose, or who are unwilling to attempt a dose reduction within the allowed range, will be discontinued from the study.

The reason and information for study drug discontinuation will be recorded on the appropriate CRF.

Subjects who prematurely terminate the study participation will not be replaced.

Every effort should be made for all subjects prematurely discontinuing the study drug, regardless of cause, to undergo final evaluation procedures described in [Section 11.5.11](#).

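### For an uncomplicated confirmed pregnancy, Section 12.4.2 ends study drug at the positive test while the discontinuation sections call for a taper

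*Protocol*

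**What the plan says.** Protocol Section 12.4.2 takes a reported pregnancy in steps. First, "All female pregnant subjects will be instructed to commence discontinuation of the study medication". The subject is then asked to come back promptly, within 48 hours, for a confirmatory test. Next: "If positive, the female pregnant subject will no longer receive any additional study medication". The section goes on to require follow-up of every pregnancy, whether or not more study drug was taken. On AE status it says: "Pregnancy itself is not regarded as an AE unless there is a suspicion that the study drug may have interfered" with a contraceptive, or unless other AEs were detected. The taper is not mentioned.

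The discontinuation text is general. Section 10.1.2 says that subjects who stop ESL before Visit 9 "for any reason will be gradually tapered off study drug (see Table 5"; an abrupt stop is allowed for treating an AE. Section 13 says: "Subjects who discontinue the study will undergo taper of study drug, unless abrupt discontinuation of the drug is required in response to an AE". The synopsis and Section 7.1 carry the same rule with the same single exception. Footnote p of Table 2 adds: "Subjects who discontinue prior to the EOS visit will be provided sufficient ESL to accommodate the appropriate taper regimen". Section 13 lists pregnancy as a reason for discontinuation, separately from adverse event.

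**The concern.** A site that opens Section 12.4.2 finds that no more drug is given once the test is positive. A site that opens Section 10.1.2 or 13 finds that the subject is tapered unless an AE calls for an abrupt stop. Neither text refers to the other, and none of the taper passages names pregnancy as an exception.

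What is at stake is subject safety and uniform conduct. The subjects have uncontrolled seizures, and the manner of withdrawing an antiepileptic drug in a pregnant subject should not depend on which section is consulted. Pregnancy is also foreseeable here: women of childbearing potential are tested at screening and at each site visit through Visit 9.

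**Working it through.** The plan states no figure to reproduce. The check sets the passages side by side and adds the dosing implied by Table 5.

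**1. Does a taper passage exempt pregnancy?** No. The synopsis and Sections 7.1, 10.1.2 and 13 each name an AE as the sole ground for an abrupt stop. Footnote p has no exception.

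**2. Does the AE exception take in pregnancy?** Not in general. Section 12.4.2 makes pregnancy an AE matter only where contraceptive interference is suspected or other AEs are detected. Even then, the taper sections allow an abrupt stop only where the AE calls for it. An uncomplicated pregnancy stays outside the exception.

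**3. Can Section 12.4.2 be read as starting a taper?** If the instruction to commence discontinuation means that the taper begins at notification, the confirmatory test follows within 48 hours and the positive result then ends further drug. A subject who returns on time would have had about 2 days of a taper that Table 5 sets at 7 or 14 days.

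**4. Can it be read as ending dispensing only?** Then it disagrees with footnote p, which provides drug for the taper.

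**5. Size of the difference** (Table 5, 7 days per taper week):

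| Dose at stopping | Taper | Days | Total ESL | Section 12.4.2, literally |
|---|---|---|---|---|
| 800 mg/day | 400 for 1 week | 7 | 7 × 400 = 2,800 mg | 0 days, 0 mg |
| 1200 or 1600 mg/day | 800 for 1 week, then 400 for 1 week | 14 | 7 × 800 + 7 × 400 = 8,400 mg | 0 days, 0 mg |

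**6. Effect on the analyses.** Section 10.1.2 withdraws a subject who stops early, whether abruptly or by taper. SAP Section 15.1.1 counts as completers those who reach the end of the Maintenance Phase at Visit 9, over the safety population. A subject withdrawn before Visit 9 is therefore in the denominator and not in the numerator under either rule, and retention does not move. Duration of exposure (SAP Section 14) and time on ESL (SAP Section 15.2.1.5) run to the last dose. If the recorded last dose is the last taper dose, which the SAP does not specify, both shift by 7 or 14 days for that subject.

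**The case against.** The best defence is that Section 12.4.2 never prescribes an abrupt stop. To commence discontinuation describes a process, and the follow-up sentence allows that some pregnant subjects take more drug after the pregnancy is known. On that reading the section ends continued treatment and leaves the manner of stopping to Section 10.1.2, so the fault is a missing cross-reference. This has some force, and it shows the section is unclear. It does not remove the literal conflict, because the sentence on the positive test carries no allowance for a taper.

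Exposure is also limited. Subjects who are pregnant or intend pregnancy are excluded, pregnancy is immediately reportable to the sponsor, and the Medical Monitor is the contact for protocol questions. That makes inconsistent handling less likely without curing the wording.

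A reader might infer more than the text supports on four counts:

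- **That every pregnancy is caught.** The AE clause in Section 12.4.2 has two exceptions, and in those cases the AE route to an abrupt stop may be open.
- **That sites are ordered to dispense a taper.** The Early Discontinuation Visit list (Section 11.5.11) and the IXRS option (Section 9.3) both supply drug only if it is needed for taper, so they fit either rule. Footnote p is firmer.
- **That partner pregnancy is a second contradiction.** Section 13 lists "Pregnancy (subject or subject's partner") among reasons for which subjects may be discontinued. The list is permissive, and Section 12.4.2, which stops drug only for the pregnant subject, does not contradict it.
- **That retention is affected.** It is not, as step 6 of the working shows.

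**Conclusion.** The point holds for an uncomplicated confirmed pregnancy: read literally, Section 12.4.2 and the taper passages cannot both be followed. The difference is 7 days and 2,800 mg, or 14 days and 8,400 mg, against no further drug. It is a wording inconsistency that bears on subject safety, not a flaw in the analysis. The only statistical trace is a possible shift of up to 14 days in last-dose date, exposure and time on ESL for the subjects concerned.

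This assumes that Section 12.4.2 is taken at its word and that the subject is on a dose listed in Table 5, which has no row for 400 mg/day. The documents give no expected number of pregnancies. Few are likely, and the conclusion does not depend on the count. Nothing here says which instruction is right.

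**What to change.** Reconcile Section 12.4.2 with the synopsis, Sections 7.1, 10.1.2 and 13, Table 5 and footnote p of Table 2, so that a single instruction on how ESL is stopped applies to a confirmed pregnancy. If pregnancy is meant to be an exception to the taper, the taper passages should name it. If it is not, the sentence on the positive test should be reworded and should refer to Section 10.1.2. The sponsor's clinical team decides which rule stands. Footnote p is repeated in SAP Section 3.5, and that copy should follow any change.

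The cost is protocol wording and a note to sites. No visit, procedure or analysis is added.

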13. TERMINATION OF SUBJECT FROM STUDY

Subjects may terminate the study participation at any time for any reason.

Subjects may be discontinued from the study at any time for any of the following reasons:

- Adverse event.
- Lack of efficacy (specify).
- Withdrawal by subject (specify).
- Withdrawal by Investigator (specify).
- Protocol deviation (specify).
- Study terminated by Sponsor.
- Death.
- Pregnancy (subject or subject's partner).
- Other (specify).

If at any time during the course of the study, in the opinion of the Investigator, the subject may no longer safely participate due to a change in medical status (eg, experiences an AE, becomes pregnant), the subject must be discontinued from the study.

Subjects may discontinue the study at any time due to worsening of seizures, intolerance, or other reasons.

Subjects who discontinue the study will undergo taper of study drug, unless abrupt discontinuation of the drug is required in response to an AE (eg, rash).

Subjects who experience an intolerable AE at the lowest dose, or who are unwilling to attempt a dose reduction within the allowed range, will be discontinued from the study.

The reason and information for study drug discontinuation will be recorded on the appropriate CRF.

Subjects who prematurely terminate the study participation will not be replaced.

Every effort should be made for all subjects prematurely discontinuing the study drug, regardless of cause, to undergo final evaluation procedures described in [Section 11.5.11](#).

14. STUDY TERMINATION

The Sponsor reserves the right to discontinue the study at this study center or at multiple centers for safety or administrative reasons at any time while safeguarding that early termination does not compromise subjects' safety or well-being. In particular, a study center that does not recruit at an acceptable rate may be closed. Should the study be terminated and/or the study center closed for whatever reason, all documentation must be returned to the Sponsor or its representative.

If, in the opinion of the Investigator, clinical observations suggest it may be unsafe to continue, the Investigator may terminate part or the entire study after consultation with the Sponsor.

15. STATISTICS

15.1. Sample Size

Sample size is calculated based on the precision (a half width of the 95% confidence interval [CI]) for the estimate of the completion rate as assumed as below and is used the Normal approximation to the Binomial distribution.

Arm 1 (first add-on): Assuming a completion rate of 60% at 24 weeks of the Maintenance Phase for Arm 1, to show the lower limit of the 95% CI in the rate to be 50% (50%, 70%), the sample size is estimated at approximately 93 subjects.

Arm 2 (later add-on): Assuming the completion rate of 50% at 24 weeks of the Maintenance Phase for Arm 2, to show the lower limit of the 95% CI in the rate to be 40% (40%, 60%), the sample size is estimated at approximately 97 subjects.

Total estimated subject enrollment is approximately 190 subjects.

15.2. Analysis Populations

The safety population will consist of all subjects who have taken any study medication and will be used for all analyses except efficacy analyses.

The modified intent-to-treat (mITT) population will include subjects who are in the safety population and have available seizure data. The mITT population will be used for efficacy analyses.

15.3. Data Analysis

The Statistical Analysis Plan provides details on the statistical methods planned for this study and will be finalized prior to the database lock. Statistical summaries described in sections below will primarily be provided for all subjects (ie, overall summary) in the analysis populations of interest unless otherwise stated.

All endpoints will be summarized descriptively for Arm 1 and Arm 2 separately. There will be no statistical comparisons between Arm 1 and Arm 2.

For the efficacy endpoints, baseline will be defined as the seizure data for the longest available period up to 3 months prior to screening from seizure history and from screening to first dose of study medication from the paper seizure diary.

For all other endpoints, baseline will be defined as the last non-missing measurement taken prior to the first dose of study drug administration.

15.3.1. Subject Disposition

Subject disposition will be summarized and presented for the number and percentage of subjects, who were screened, screen-failed, completed the study, and discontinued early (including reasons for discontinuations).

15.3.2. Drug Exposure

The number of doses taken as well as the extent of exposure will be summarized with descriptive statistics and presented. For each subject, the number of doses taken will be computed. The extent of exposure will be computed as the number of days from the first exposure to study drug to the last exposure to study drug, ignoring missing days. Average daily dose will also be calculated.

15.3.3. Important Protocol Deviations

Important protocol deviations (IPDs) will be identified and documented based on a review of potentially IPDs. The potentially IPDs will be identified shortly before database lock, either through programmatic checks of study data (eg, inclusion/exclusion criteria violations), as well as through review of selected data listings (eg, Investigator comments, concomitant medications). The potentially IPDs to be reviewed include, but are not limited to, subjects who:

- Did not meet inclusion/exclusion criteria or eligibility was not adequately verified.
- Received any prohibited concomitant medication.
- Developed study withdrawal criteria but were not withdrawn.

Individual IPDs will be presented in a data listing. The number and percentage of subjects with IPDs will be summarized by type of deviation as categorized above.

15.3.4. Demographics and Baseline Characteristics

Demographics, including (age, gender, race, and ethnicity where applicable), and other baseline characteristics collected at screening, such as height, weight, body mass index, and disease conditions will be summarized using descriptive statistics. These data will be presented as a listing.

15.3.5. Primary Analysis

The proportion of subjects completing 24 weeks adjunctive therapy during Maintenance Phase and the 95% CI will be calculated for Arm 1 and Arm 2 separately.

15.3.6. Efficacy Analyses

All efficacy endpoints will be summarized descriptively in this study. Changes in efficacy parameters will be calculated with reference to the baseline, defined as the seizure data for the longest available period up to 3 months prior to screening from seizure history and from screening to first dose of study medication from the paper seizure diary.

All seizure related endpoints will be calculated based on the data from the paper diary.

Seizure frequency will be standardized to 28-day rate. The SSF and changes from baseline will be summarized during the first 12 weeks, the last 12 weeks, and the 24 weeks of the Maintenance Phase.

Two responder rates (50%, and 75% responder rates) are defined as subjects who have $\geq 50\%$, and subjects who have $\geq 75\%$ reduction in SSF from baseline, respectively. The proportions of

responders in each rate will be summarized during the first 12 weeks, the last 12 weeks, and the 24 weeks of the Maintenance Phase.

Relative reduction (%) in SSF from baseline will be calculated during the first 12 weeks, the last 12 weeks, and the 24 weeks of the Maintenance Phase.

The proportion (%) of seizure-free subjects will be provided during the first 12 weeks, the last 12 weeks, and the 24 weeks of the Maintenance Phase.

Time on ESL will be calculated from the first dose to the last known dose of ESL. The median time and 95% CI will be estimated using Kaplan Meier time to event methods. Subjects who were still on ESL at the end of study will be censored at the end of study. Subjects who dropped out of the study while receiving treatment will be an event at the time of the dropout. Change in dosage levels during the treatment period will be ignored.

15.3.7. Other Analyses

15.3.7.1. Neurological Disorders Depression Inventory for Epilepsy Score

The NDDI-E score and change from baseline for each evaluation time point will be summarized descriptively.

15.3.7.2. Profile of Mood States Short-form Score

The POMS-SF scores and changes from baseline for each evaluation time point will be summarized descriptively.

15.3.7.3. Mood States Short-form Score

The MOAS scores and changes from baseline for each evaluation time point will be summarized descriptively.

15.3.7.4. Quality of Life in Epilepsy-Patient-Weighted Score

The QOLIE-31-P scores and changes from baseline for each evaluation time point will be summarized descriptively.

15.3.7.4.1. EuroQol Five Dimensions Questionnaire Score

The EQ-5D scores and changes from baseline for each evaluation time point will be summarized descriptively.

15.3.7.5. Clinical Global Impression of Improvement Score

The CGI-I score for each evaluation time point will be summarized descriptively.

15.3.7.6. Patient's Global Impression of Change Score

The PGI-C score for each evaluation time point will be summarized descriptively.

15.3.8. Safety Analyses

15.3.8.1. Adverse Events

All AEs will be coded using Medical Dictionary for Regulatory Activities (MedDRA) version 13.1 or higher. AEs are untoward medical occurrences:

- that occurred on or after the first dose of study medication.
- with a missing start date and a stop date on or after the first dose of study medication,
OR
- with both a missing start and stop date.

AEs will be summarized by MedDRA system organ class (SOC) and Preferred Term (PT).

The following AEs will be summarized and presented by MedDRA SOC and PT for the Safety population:

- All AEs (including number of events and subject incidence).
- AEs by severity (mild, moderate, severe).
- AEs by relationship to the study treatment (related, or not related).

The following conventions will be followed in summarizing AEs:

- For subject incidence summaries, each subject will be counted only once within each SOC and within each PT.
- If a subject reports more than one AE within a PT and/or a SOC, the AE with the highest known severity within each SOC and within each PT will be included in the summaries by severity.
- For summaries by relationship to the study medication, AEs will be grouped as “related” or “not related.” AEs assessed as “possible,” “probable,” or “definite,” will be grouped as “related.” If a subject reports more than one AE SOC and PT, and any are related, it will be summarized as related.

Summaries of SAEs, AEs leading to discontinuation or other AE summaries will also be provided if necessary. A listing of AEs, as well as a listing of deaths, SAEs, and AEs leading to discontinuation, will be presented.

